4.8. Safety Analyses

Safety analyses will be conducted using the Safety Population.

4.8.1. Extent of treatment exposure and compliance

Sponsor:	ObsEva		
Protocol:	18-OBE2109-003		
Document Version No.:	V5.0	Document Date:	13-JUN-2022

4.8.1.1. Extent of treatment exposure

Duration of treatment (in weeks and in days) will be summarized for each treatment group. Duration is defined as: [(date of last treatment administration as described in section 4.2.11) - (date of first administration as collected in eCRF) +1] / 7 (weeks), [(date of last treatment administration as described in section 4.2.11) - (date of first administration as collected in eCRF) +1] (days).

Time on study (in weeks and in days) will be summarized for each treatment group, defined as: [(end of study date as described in section 4.2.11) – (first dose date) +1.]/7 (weeks), [(end of study date as described in section 4.2.11) – (first dose date) +1.] (days).

Exposure data will be reported in listings.

4.8.1.2. Compliance

Lingazolix/Placebo Grey blister (200 mg or matching placebo), Lingazolix/Placebo Pink blister (75 mg or matching placebo) and Add-back therapy compliance from the study treatment accountability page will be averaged among the Day 1-Month 3 and Month 3-End of study periods and summarized by treatment group.

If Lingazolix/Placebo and Add-back therapy compliance from accountability data are missing, compliance will be computed from daily e-diary data for the corresponding 3-month period. Compliance will be computed as the number of days with pink tablet/grey tablet/red capsule taken divided by the number of days in the period (Month 3 visit date/early discontinuation visit date-Day 1 or Month 6 visit date/early discontinuation visit date-Month 3 visit date). Data from "Today" will be used primarily. If data from today is missing, data from "Yesterday" will be considered. If the e-diary is not completed for a day (neither "Today" nor "Yesterday), it will be assumed that no intake of drug was taken on that day.

Study treatment overdose and misuse will be reported in a listing.

Compliance will be reported in a listing.

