Document Version No.:	V5.0	Document Date:	13-JUN-2022

Pharmacokinetic (PK) Set: all subjects who received active study medication, had no major protocol deviations impacting PK evaluation and with available PK data.

In general, analyses of efficacy will be conducted using the FAS, PP and FU sets, analyses of safety will be conducted using the Safety Set and FU SAF, and analyses of PK will be conducted using the PK Set.

The actual treatment will be derived as follows, based on daily e-diary IMP intake data:

Subjects received a different kit of active linzagolix or placebo for each month, and a different kit for addback or placebo for each 3-month period.

The number of days with one pink tablet, one grey tablet and one red capsule taken based on e-diary IMP intake data for each treatment will be computed. Data from "Today" will be used primarily. If data from today is missing, data from "Yesterday" of the following day will be considered. If the e-diary is not completed for a day (neither "Today" nor "Yesterday" of following day), it will be assumed that no intake of drug was taken on that day.

Further rules are as follows:

- Treatment administration errors:
 - If a subject received placebo with placebo ABT in more than 50% of days, then the actual treatment group will be placebo with placebo ABT.
 - Otherwise, the active treatment group (combined with add-back or placebo add-back) with the most days taken will be assigned.
 - If the number of days is equal for two treatments groups containing active treatment then LGX 200 mg with ABT will be assigned.
- If a subject discontinued, only data received up to discontinuation will be used.
- It is possible that the derived actual treatment group does not correspond to any of the planned treatment groups. In that case actual treatment group will be assigned to the planned treatment group with same dose of active treatment. Example: LGX 75mg with ABT will be assigned to LGX 75mg with placebo ABT; LGX 200mg with placebo ABT will be assigned to LGX 200mg with ABT. A listing with such cases will be provided.

3.2. **Protocol Violations**

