A protocol deviation is any noncompliance with the clinical trial protocol or International Conference on Harmonization Good Clinical Practice (ICH GCP) requirements. It is the responsibility of the site investigator to use continuous vigilance to identify and report deviations. All deviations must be addressed in study source documents and reported to the reviewing IRB/IEC per their policies. The site investigator is responsible for knowing and adhering to the reviewing IRB/IEC requirements.

Sponsor:	ObsEva		
Protocol:	18-OBE2109-003		
Document Version No.:	V5.0	Document Date:	13-JUN-2022

All Protocol Deviations will be reported to the Sponsor and documented in the monitoring report. These will be classified as minor or major based on their effect on the right, safety or well-being of the subjects and/or the quality and integrity of the data, and the final rating of all deviations will be confirmed prior to database lock. The final protocol deviation file (formatted as a Microsoft Excel file) will be provided to Cytel.

Major protocol deviations will be summarized by category (if available) and by treatment group for the FAS population.

Major deviations that could potentially affect the efficacy assessments up to Month 6 and thus may exclude subjects from the PP Set may include:

- Non-compliance with inclusion criteria 3; 6; 8
- Non-compliance with exclusion criteria 2 to 10 inclusive; 12; 13; 17; 19; 20; 21; 23; 24; 25
- Non-compliance with study treatment: threshold to be defined during blinded data review meeting (e.g. IMP compliance in tablets <60% for Day1-Month 6)
- IP Dispensing error;
- Unauthorised prior or concomitant therapy;
- M3 and/or M6 Visits performed outside the +/-14 days of the theoretical visit date;
- Randomisation code broken;

All protocol deviations will be presented in the data listings.

Sponsor:	ObsEva		
Protocol:	18-OBE2109-003		
Document Version No.:	V5.0	Document Date:	13-JUN-2022

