7.5. Appendix E: Mapping rules for ediary data

Table 8 Mapping Rules for

Device

Cas e #	impacte d visit	Patient status	Schedul e of daily diary	impact on data	Cytel action on IMP intake data	Cytel action on Menstrual data	Cytel mapping	cut off date (from eCRF)
1	Month 6	patient was included in EXT	remain ed in MAIN TREAT MENT (due to Covid remote visit or to site error in diary comple tion)	data present in the Main datasets should be considere d for the analysis of the extension study	mapping	n/a	from MAIN TREAT to EXT TREAT	First IMP intake in EXT

Sponsor:	ObsEva			
Protocol:	18-OBE2109-003			
Document Version No.:	V5.0	Document Date:	13-JUN-2022	

2	Month 6	patient was included in EXT	resched uled to MAIN FU (due to site error in diary comple tion)	data present in the Main datasets should be considere d for the analysis of the extension study	n/a - missing in final DB	n/a	from MAIN FU to EXT TREAT	First IMP intake in EXT
3	Month 6	patient entered MAIN FU	resched uled to EXT TREAT MENT (site error in diary comple tion)	data present in the Extension datasets should be considere d for the analysis of the Main study	"Is the subject eligible to the 6 months treatment free follow-up?" is YES> delete answers to YIMPI and IMPI	n/a	from EXT TREAT to MAIN FU	MONTH 6 visit date

 Sponsor:
 ObsEva

 Protocol:
 18-OBE2109-003

Document Version No.:	V5.0	Document Date:	13-JUN-2022

4	Month 6	patient entered MAIN FU	remain ed in MAIN TREAT MENT (due to Covid remote visit or to site error in diary comple tion)	Data regarding IMP intake will be present for this period	"Is the subject eligible to the 6 months treatment free follow-up?" is YES> delete answers to YIMPI and IMPI	n/a	n/a - remain in MAIN DB	MONTH 6 visit date
5	Month 6	whatever status: DUPLICATE ENTRIES	patient entered diary data in both Main and Extensi on studies each day	duplicate s data will be present across the datasets	CASE by CASE review	- cleaning nee	ded	

Sponsor:	ObsEva			
Protocol:	18-OBE2109-003			
Document Version No.:	V5.0	Document Date:	13-JUN-2022	

6	Day 1	patient entered MAIN TREATMENT	remain ed in SCREEN ING (due to site error in diary comple tion)	Data regarding IMP intake will not be present for this period and data regarding menstrua I periods will be present	n/a - missing in final DB	delete the answers to "is it your Menstrual period?" and start date questions, if any	n/a - remain in MAIN DB	First IMP intake in MAIN

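### When accountability data are missing, the diary compliance rate counts days after the last dose and days on which the diary could not record intake, so a fully compliant woman can score below 100%.

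*SAP*

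**What the plan says.** SAP 4.8.1.2 takes compliance from the study treatment accountability page. It is averaged over Day 1 to Month 3 and over Month 3 to end of study, then summarized by treatment group and listed. The diary is used only as a fallback, when "compliance from accountability data are missing, compliance will be computed from daily e-diary data". The fallback rule is: "Compliance will be computed as the number of days with pink tablet/grey tablet/red capsule taken divided by the number of days in the period". The period is defined as "Month 3 visit date/early discontinuation visit date-Day 1 or Month 6 visit date/early discontinuation visit date-Month 3 visit date". If the diary has neither a same-day entry nor a next-day entry covering a given day, "it will be assumed that no intake of drug was taken on that day".

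Three other parts of the SAP bear on this:

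- Exposure duration, in SAP 4.8.1.1 just before, ends at the "date of last treatment administration as described in section 4.2.11" and adds one day so that both end dates count.
- The derivation of actual treatment in SAP 3.1 uses the same diary intake data but adds a cut: "If a subject discontinued, only data received up to discontinuation will be used".
- Appendix E, Table 8, case 6 covers women already on treatment whose device stayed in screening mode through site error. It says "Data regarding IMP intake will not be present for this period" and treats the intake data as missing in the final database.

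SAP 3.2 lists treatment non-compliance among the deviations that may exclude a subject from the Per Protocol Set. The threshold is left to the blinded data review, with the example "IMP compliance in tablets <60% for Day1-Month 6".

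**The concern.** A compliance rate should compare doses taken with doses that were due and could be recorded. The fallback departs from this in two ways.

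First, for an early stopper the denominator runs to a visit date. Days between the last dose and that visit can add nothing to the numerator, yet they count as days of non-compliance. The SAP avoids this for exposure and for actual treatment, but not here.

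Second, the numerator counts only days with recorded intake, while the denominator is calendar time. Days on which the device did not present the intake question are therefore scored as missed doses. The SAP documents this device fault in Appendix E but does not carry it into SAP 4.8.1.2.

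At stake is a reported compliance figure. If early stopping differed between arms and accountability data were missing for some of those women, part of that difference would appear as a difference in compliance. For a completer with a long device fault, the figure could also affect Per Protocol membership.

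**Working it through.** The documents state no compliance figure, so there is none to reproduce. The check applies the SAP formula to a woman who takes every dose, so that her true compliance is 100%.

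**Inputs**

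- Month 3 is Day 85 and Month 6 is Day 169 (SAP 4.2.9, Table 3), so each period has 84 days.
- Dosing is once daily from Day 1 to the day before the Month 6 visit (protocol 11.2).
- Gap *g* is the number of days from last dose to discontinuation visit. Protocol 10.5 and 10.7.2 foresee withdrawal visits with no dose the day before, but give no length. Assumed range: 0 to 28 days.
- Fault length *s* is the number of days in screening mode with intake not recovered. It is not given. Assumed range: 3 to 84 days.

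**Completer with a working diary.** First period: 84/(85 − 1) = 100%. Second period: 84/(169 − 85) = 100%. If the Month 3 visit-day dose were counted in the first period, that period would give 85/84 = 101.2%.

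**Early stopper.** With *L* dose days and a visit *g* days after the last dose, the visit falls on Day *L* + *g*. Compliance is *L*/(*L* + *g* − 1). The same formula holds for dose days counted from Month 3.

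| Dose days *L* | *g* = 1 | *g* = 3 | *g* = 7 | *g* = 14 | *g* = 28 |
|---|---|---|---|---|---|
| 14 | 100% | 87.5% | 70.0% | 51.9% | 34.1% |
| 28 | 100% | 93.3% | 82.4% | 68.3% | 50.9% |
| 42 | 100% | 95.5% | 87.5% | 76.4% | 60.9% |
| 70 | 100% | 97.2% | 92.1% | 84.3% | 72.2% |

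For example, 42/(42 + 7 − 1) = 42/48 = 87.5%, and 42/(42 + 14 − 1) = 42/55 = 76.4%. A visit on the day of the last dose gives more than 100%: 42/41 = 102.4%.

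**Diary in screening mode, first period.** Compliance is (84 − *s*)/84:

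- *s* = 3: 96.4%
- *s* = 7: 91.7%
- *s* = 14: 70/84 = 83.3%
- *s* = 28: 56/84 = 66.7%
- *s* = 84: 0%

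**Same fault, Day 1 to Month 6.** Compliance is (168 − *s*)/168, so *s* = 28 gives 83.3% and *s* = 56 gives 66.7%. To fall below the example 60% threshold, *s* must reach 68: 101/168 = 60.1% at *s* = 67, and 100/168 = 59.5% at *s* = 68. A woman who truly took 75% of doses (an assumed figure) would cross at *s* = 34: 0.75 × 134/168 = 59.8%.

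**Per Protocol membership.** SAP 3.1 limits the Per Protocol Set to subjects who completed six months of treatment. An early stopper is outside it whatever her compliance rate.

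**With the correction.** An early stopper's denominator becomes last dose date − period start + 1 = *L*, giving *L*/*L* = 100%. With unasked days removed, the device-fault case gives (84 − *s*)/(84 − *s*) = 100% for *s* below 84. At *s* = 84 no evaluable day remains and the rate is missing.

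**The case against.** The strongest reply is that this is a rarely used rule for a descriptive result. Accountability is based on blisters, is done at each visit and is checked by the monitor (protocol 10.2.2, 11.5 and 11.7). The error needs missing accountability data together with either a delayed exit visit or a wrongly set device, and the documents give no frequency for any of these. Compliance is not tested. This stands, and it limits the point to a small one.

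A reader might infer that fully compliant women in general score well below 100%. The documents do not support that: a completer with a working diary scores 100%, and so does an early stopper seen the day after her last dose.

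A reader might also infer that early stoppers would be wrongly dropped from the Per Protocol Set. They are already outside it. For completers, 60% is only an example, the listed deviations only may exclude a subject, and the SAP does not say whether compliance in tablets would use the diary fallback at all. A fault from Day 1 lasting 68 days would also have to survive the diary checks at Months 1 and 2.

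Finally, Table 8 case 6 describes one device. For the same fault on the second device (Table 9, cases 5 and 6), the stated action on intake data is mapping. That may recover the data, but the table also says they are absent and does not explain how they would be recovered.

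None of this removes the defect. Followed as written, the rule gives a wrong figure for the women to whom it applies.

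**Conclusion.** The fallback rule is wrong as written, with small consequences. It can understate compliance for an early stopper whose exit visit falls more than one day after her last dose, and for a woman whose diary stayed in screening mode while she was taking drug. The shortfall depends on the length of the gap or fault. A 3-day gap costs about 3 to 13 points and a 14-day gap about 16 to 48 points, for 70 down to 14 dose days. These sizes rest on assumed lengths and on full compliance, and apply only where accountability compliance is missing.

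The early-stopper error affects only the compliance summary and listing. The diary-fault error could affect Per Protocol membership only for a completer with a long fault: about 68 or more of 168 days if she is otherwise fully compliant and the example threshold is adopted. It would be tempting to read this as a threat to the primary result. It is not: the co-primary analysis uses the Full Analysis Set by randomized treatment, whatever the compliance (SAP 4.6.2.1).

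**What to change.** In SAP 4.8.1.2:

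1. For early stoppers, end the denominator at the last treatment administration date already defined in SAP 4.2.11, with the added day used in SAP 4.8.1.1. Leave the completers' denominator as it is.
2. Treat days on which the device did not present the intake question as missing, not as missed doses. This covers Table 8 case 6, and Table 9 cases 5 and 6 if mapping does not recover intake. State in Table 9 what that mapping does. Days left blank on a working diary can keep the present rule.
3. Report the number of evaluable days beside each fallback compliance rate.

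The cost is a few sentences of SAP text, a flag for screening-mode days and minor programming. The last-dose date already exists. The downside is that unasked days are then assumed to resemble asked days, which the count of evaluable days lets a reader judge.

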4.8.1.3. Question Regarding Treatment Received

Subjects were asked at treatment termination which treatment they believed they received during the blinded treatment period. The number of subjects who believed they received active treatment, placebo or unknown will be summarized by treatment group on the Safety Population.

4.8.2. Adverse Events

Adverse events will be coded using the Medical Dictionary for Regulatory Activities (MedDRA) and displayed in tables and listings using System/Organ/Class (SOC) and Preferred Term.

Sponsor:	ObsEva		
Protocol:	18-OBE2109-00	3	
Document Version No.:	V5.0	Document Date:	13-JUN-2022

Analyses of adverse events will be performed for those events that are considered treatment emergent (TEAEs), where treatment emergent is defined as AEs with a start date on or after the first dose of study drug through 30 days after discontinuation of study drug or the Month 6 date, or any event that was present at baseline but worsened in intensity or was subsequently considered drug-related by the investigator through 30 days after discontinuation of study drug or the Month 6 date.

Adverse Event tables will be presented for the following periods, as defined in Section 4.2.11:

- Day 1 to Month 6 date -1 or treatment discontinuation date (treatment period)
- Month 6 date or (treatment discontinuation date+1) to Month 6 FU (follow-up period):
 - TEAE: AEs starting within 30 days after discontinuation of study drug or Month 6 visit date
 - Post-treatment AE: Adverse events starting more than 30 days after end of treatment
- Day 1 to Month 6 FU

If, for a subject not entering the follow-up period or the extension, an AE occurs within the 30 days following Month 6 date-1 or treatment discontinuation, then the AE will be counted in the treatment period.

For each of the treatment and follow-up periods, an overall summary table will be prepared presenting, by treatment group and overall, the number and percentage of subjects with

- any TEAE,
- Severe TEAE
- any TEAE assessed by the Investigator as related to Linzagolix,
- any TEAE assessed by the Investigator as related to add-back therapy,
- any TEAE leading to permanent discontinuation of IMP,
- any serious adverse event,
- any serious Treatment Emergent Adverse Event,
- any serious Treatment Emergent adverse event related to Linzagolix,
- any serious Treatment Emergent adverse event related to add-back therapy,
- Any TEAE leading to permanent discontinuation of IMP
- any fatal TEAE (where outcome is "Fatal")

In these tabulations, each subject will contribute only once (i.e., via the most related occurrence or the most intense occurrence) to each of the incidence rates in the descriptive analysis, regardless of the number of episodes experienced.

Sponsor:	ObsEva		
Protocol:	18-OBE2109-003		
Document Version No.:	V5.0	Document Date:	13-JUN-2022

Adverse events are summarized by subject incidence rates, therefore, in any tabulation, a subject contributes only once to the count for a given adverse event (SOC or preferred term).

The number and percentage of subjects with any treatment-emergent adverse event, with any treatment-emergent adverse events assessed by the Investigator as related to treatment (definite, probable, or possible relationship), and with any treatment-emergent serious adverse event and with any treatment-emergent non-serious adverse event will be summarized by treatment group and overall. Tabulation by severity will also be made. In these tabulations, each subject will contribute only once (i.e., the most related occurrence or the most intense occurrence) to each of the incidence rates in the descriptive analysis, regardless of the number of episodes.

The ongoing status of each Adverse Event will be derived based on Adverse Event Outcome as the following:

AE Outcome	AE Ongoing Status
Fatal	No
Not recovered/not resolved	Yes
Recovering/resolving	Yes
Recovered/resolved	No
Recovered/resolved with sequelae	No
Unknown	Unknown
Missing	Missing

The ongoing status collected in eCRF will be ignored.

No formal hypothesis-testing analysis of adverse events incidence rates will be performed.

All adverse events occurring on study will be listed in subject data listings.

By-subject listings also will be provided for the following: subject deaths; serious adverse events; and adverse events leading to withdrawal.

Sponsor:	ObsEva		
Protocol:	18-OBE2109-003		
Document Version No.:	V5.0	Document Date:	13-JUN-2022

4.8.3. Bone Mineral Density (BMD) by DXA

BMD of the femoral neck, total hip and lumbar spine will be assessed by DXA at Baseline, Month 6 and Month 6 follow-up. Unacceptable DXA assessments (accepted="No") will not be summarized (hip, and spine and femur considered separately).

In case of repeated values due to BMD loss \geq 5%, the initial scan will be used in summaries. Initial and repeated scan values will be reported in the listings.

Calibrated values should be provided once all cross-calibration data are made available to the vendor in charge of the scan assessment. These calibrated values will be used in the summary tables if available, otherwise initial values will be considered.

BMD values and corresponding Z-scores will be summarized for each treatment group. The within-group percent changes from baseline for BMD values will also be summarized, including 2-sided 95% confidence intervals.

Percent change from baseline to Month 6 and Month 6 follow-up will be described and will also be summarized in categories of percent change with the following classes:

- No change or increase,
- Decrease ≤ 3%,
- Decrease > 3% and $\leq 5\%$,
- Decrease > 5% and \leq 7%,
- Decrease > 7% and \leq 8%,
- Decrease > 8%.

The percent changes from baseline to Month 6 will be compared between each of the linzagolix groups and the placebo group via analysis of covariance with treatment group as the main effect (three values) and including the baseline as a covariate.

Sample SAS code (SAS code will be fully validated at the analysis stage) for analysis of covariance:

```
Proc GLM data=dataset order=internal;
        Class Treat;
        Model BMD_pchg = BaselineBMD Treat;
        LSMEANS Treat / at means pdiff= control('1') alpha=0.05 cl adjust=bon;
        ODS OUTPUT lsmeans=lsm diff=pvals lsmeancl=lsmeancl
lsmeandiffcl=lsmeandiffcl;
Run;
```

All data will be listed.

A listing of BMD for subjects who discontinued treatment will be provided.

CRS-BS-TP-000005 V 1.0

Page 93 of 127

Cytel Confidential: This is a controlled document and shall not be changed, saved, copied or reproduced by any unauthorized

Sponsor:	ObsEva		
Protocol:	18-OBE2109-003		
Document Version No.:	V5.0	Document Date:	13-JUN-2022

Subgroup analyses by race, age groups 1 and 2, weight and BMI groups 1 and 2 will be performed for BMD, including descriptive summaries, percent changes categories summaries and analysis of covariance.

Due to the war situation in Ukraine, data from subjects in Ukraine sites may be incomplete, missing or uncleaned. A sensitivity analysis of the BMD will be performed, excluding data collected after 24FEB2022 for subjects from Ukraine sites, for the Follow-up period only (Follow-up Safety set), as the main treatment period was completed before the start of the war. Listings will contain country information to identify those subjects.

